8.1 Efficacy assessments

There are no efficacy assessments as the efficacy of fosmanogepix is not under investigation in this study.

8.2 Safety assessments

Planned time points for all safety assessments are provided in the [Schedule of assessments](#). Unscheduled clinical laboratory measurements may be obtained at any time during the study to assess any perceived safety issues.

8.2.1 Physical examinations

A complete physical examination must include head, ears, eyes, nose, mouth, skin, heart, and lung examinations, lymph nodes, and gastrointestinal, musculoskeletal, and neurological systems.

A brief physical examination must include assessments of general appearance, the respiratory, cardiovascular, and neurology systems, and subject-reported symptoms.

These physical examinations must be conducted by a physician.

Physical examination findings collected during the study will be considered source data and will not be required to be reported in the eCRF, unless otherwise noted. Any untoward physical examination findings that are identified during the active collection period and meet the definition of an AE or SAE ([Appendix 3](#)) must be reported according to the processes in Sections 8.3.1 to 8.3.3.

Height and weight will be measured and recorded at Screening only to calculate body mass index (BMI). For measuring weight, a scale with appropriate range and resolution is to be used and must be placed on a stable, flat surface. Subjects must remove shoes, bulky layers of clothing, and jackets so that only light clothing remains. They must also remove the contents of their pockets and remain still during measurement of weight. Height and weight including date and time of the measurements are to be recorded in both source documents and eCRF.

8.2.2 Vital signs

Vital signs include BP, PR, temperature, respiratory rate, and oxygen saturation.

Supine BP should be measured with the subject's (preferably dominant) arm supported at the level of the heart, and recorded to the nearest mmHg after at least 5 minutes of rest. If possible, the same arm should be used throughout the study. Blood pressure should not be taken from the arm with an intravenous infusion. Subjects should be instructed not to

speak during measurements. If an IV catheter is utilized for blood sampling collections, vital sign assessments (BP and PR) should be collected prior to insertion of the catheter.

The same properly sized and calibrated BP cuff is to be used to measure BP each time. While the use of an automated device for measuring BP and PR is acceptable, when done manually, PR is to be measured in the brachial/radial artery for at least 30 seconds. When the timing of these measurements coincides with a blood collection, BP and PR should be obtained prior to the blood collection.

Additional collection times, or changes to collection times, of BP and PR are permitted as necessary to ensure appropriate collection of safety data.

Temperature will be measured by the method according to the Investigator's discretion, provided the same method is used and documented throughout the study. No eating or drinking is allowed for 15 minutes prior to the measurement.

Respiratory rate and oxygen saturation will be measured by the method according to the Investigator's discretion, provided the same method is used and documented throughout the study.

Vital signs data (i.e., BP, PR, temperature, respiratory rate, and oxygen saturation) including date and time of the measurements are to be recorded in both source documents and eCRF.

8.2.3 Electrocardiograms

ECG values of potential clinical concern are listed in [Appendix 6](#).

Standard 12-lead ECGs utilizing limb leads with a 10-second rhythm strip should be performed at times specified in the [Schedule of assessments](#), using an ECG machine that automatically calculates HR and measures PR, QT, and QTc intervals and QRS complex. Alternative lead placement methodology using torso leads (e.g., Mason-Likar) should not be used given the potential risk of discrepancies with ECGs acquired using standard limb lead placement. All scheduled ECGs should be performed after the subject has rested quietly for at least 5 minutes in a supine position. If an IV catheter is utilized for blood sampling collections, ECGs should be collected prior to insertion of the catheter.

To ensure the safety of the subjects, a qualified individual at the clinical site must compare ECG results with baseline measurements. Additional ECG monitoring is to be performed if a) a post-dose QTcF interval is increased by ≥ 60 msec from the baseline and is > 450 msec; or b) an absolute QT value is ≥ 500 msec for any scheduled ECG. If either of these conditions is met, two additional ECGs are to be performed approximately 2 to 4 minutes apart to confirm the original measurement. If the QT/QTcF values from these repeated ECGs remain above the threshold values, then a single ECG must be repeated at least hourly for a maximum of 4 hours until QT/QTcF values from two successive ECGs fall below the threshold value that triggered the repeat measurement.

If a) a postdose QTcF interval remains ≥ 60 msec from the baseline and is > 450 msec; or b) an absolute QT value is ≥ 500 msec for any scheduled ECG for more than 4 hours

(or sooner, at the discretion of the Investigator); or c) QTcF intervals get progressively longer, the subject should undergo continuous ECG monitoring. A cardiologist should be consulted if QTcF intervals do not return to below these criteria after 8 hours of monitoring (or sooner, at the discretion of the Investigator).

In some cases, it may be appropriate to repeat abnormal ECGs to rule out improper lead placement as contributing to the ECG abnormality. It is important that leads be placed in the same positions each time to achieve precise ECG recordings. If a machine-read QTc value is prolonged, as defined above, repeat measurements may not be necessary if a qualified medical provider's interpretation determines that the QTcF values are in the acceptable range.

ECGs must be assessed by the investigator/designee for any abnormalities, including prolongation of QTcF. The ECG printouts are to be signed and dated by the Investigator. ECG data, including date and time of the measurements, are to be recorded in the eCRF.

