13. Screening supine 12-lead ECG demonstrating clinically-relevant abnormalities that may affect subject safety or interpretation of study results (e.g., QTcF interval > 450 msec, QRS interval > 120 msec, complete left bundle branch block, signs of an acute or indeterminate-age myocardial infarction, ST-T interval changes suggestive of myocardial ischemia, second- or third-degree AV block, or serious bradyarrhythmias or tachyarrhythmias).
14. Subjects with any of the following abnormalities in clinical laboratory tests at Screening, as assessed by the local laboratory and confirmed by a single repeat test, if deemed necessary:
 - AST or ALT $\geq 1.0 \times \text{ULN}$
 - Total bilirubin $\geq 1.5 \times \text{ULN}$; subjects with a history of Gilbert's syndrome may have direct bilirubin measured and would be eligible for this study provided the direct bilirubin level is $\leq \text{ULN}$.

Other exclusions

15. History of alcohol abuse or binge drinking and/or any other illicit drug use or dependence within 6 months of Screening. Binge drinking is defined as a pattern of \geq five (for males) or \geq four (for females) units of alcoholic drinks in 2 hours. Alcohol abuse is defined as alcohol intake exceeding 14 units per week, where 1 unit = 240 mL of beer, 30 mL of 40% spirit, or 90 mL of wine.
16. Blood donation (excluding plasma donations) of approximately 500 mL or more within 60 days prior to first dosing and until the follow-up contact.
17. Use of tobacco or nicotine-containing products in excess of the equivalents of five cigarettes per day or two chews of tobacco per day.
18. History of sensitivity to heparin or heparin-induced thrombocytopenia.
19. Unwilling or unable to comply with the criteria in Section 5.3 Lifestyle considerations.
20. Investigator site staff or Sponsor employees directly involved in the conduct of the study, site staff otherwise supervised by the Investigator, or their respective family members.

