7.1.1 ECG changes

A subject who meets either of the following criteria based on the average of triplicate ECG readings must be discontinued from the study drug.

- QTcF \geq 500 msec or
- Change from baseline: QTcF \geq 60 msec and QTcF $>$ 450 msec.

If a clinically significant ECG finding is identified (including, but not limited to, changes from baseline in QTcF after enrollment), the Investigator or designee must determine whether the subject may continue in the study, and whether any change in management is needed. In such cases the review of the ECG printed at the time of collection must be documented, and any new clinically relevant finding must be reported as an AE.

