Appendix 6 ECG findings of potential clinical concern

ECG findings that may qualify as adverse events

- Marked sinus bradycardia (rate < 40 bpm) lasting minutes
- New PR interval prolongation > 280 msec
- New prolongation of QTcF to > 480 msec (absolute) or by ≥ 60 msec from baseline
- New-onset atrial flutter or fibrillation, with controlled ventricular response rate: i.e., rate < 120 bpm
- New-onset type I second-degree (Wenckebach) AV block of > 30 seconds' duration
- Frequent PVCs, triplets, or short intervals (< 30 seconds) of consecutive ventricular complexes

ECG findings that may qualify as serious adverse events

- QTcF prolongation > 500 msec
- New ST-T changes suggestive of myocardial ischemia
- New-onset left bundle branch block (QRS > 120 msec)
- New-onset right bundle branch block (QRS > 120 msec)
- Symptomatic bradycardia
- Asystole:
 - In awake, symptom-free subjects in sinus rhythm, with documented periods of asystole ≥ 3.0 seconds or any escape rate < 40 bpm, or with an escape rhythm that is below the AV node.
 - In awake, symptom-free subjects with atrial fibrillation and bradycardia with one or more pauses of at least 5 seconds or longer.
 - Atrial flutter or fibrillation, with rapid ventricular response rate: rapid = rate > 120 bpm.
- Sustained supraventricular tachycardia (rate > 120 bpm) ('sustained' = short duration with relevant symptoms or lasting > 1 minute)
- Ventricular rhythms > 30 seconds' duration, including idioventricular rhythm (heart rate < 40 bpm), accelerated idioventricular rhythm (HR 40 bpm to < 100 bpm), and monomorphic/polymorphic ventricular tachycardia (HR > 100 bpm [such as torsades de pointes])
- Type II second-degree (Mobitz II) AV block
- Complete (third-degree) heart block

ECG findings that qualify as serious adverse events

- Change in pattern suggestive of new myocardial infarction
- Sustained ventricular tachyarrhythmias (> 30 seconds' duration)
- Second- or third-degree AV block requiring pacemaker placement
- Asystolic pauses requiring pacemaker placement
- Atrial flutter or fibrillation with rapid ventricular response requiring cardioversion
- Ventricular fibrillation/flutter
- At the discretion of the Investigator, any arrhythmia classified as an adverse experience

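### The repeat-ECG trigger uses uncorrected QT of 500 msec while the stopping rule uses QTcF of 500 msec on a triplicate average; at baseline QTcF above 440 msec the triplicate is not always required

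*Protocol*

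**What the plan says.** **Stopping rule (Protocol 7.1.1).** A subject who meets either of two criteria "based on the average of triplicate ECG readings must be discontinued from the study drug". The first criterion is QTcF of at least 500 msec. The second, "Change from baseline: QTcF", is a rise of at least 60 msec together with QTcF above 450 msec.

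**Repeat trigger (Protocol 8.2.3).** Limb (a) is met when "a post-dose QTcF interval is increased by ≥ 60 msec from the baseline and is > 450 msec". Limb (b) follows: "or b) an absolute QT value is" at or above 500 msec on any scheduled ECG. If either is met, "two additional ECGs are to be performed approximately 2 to 4 minutes apart to confirm the original measurement". If values stay above threshold, hourly ECGs follow. Continuous monitoring comes next, and its trigger again uses uncorrected QT in limb (b).

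**Number of readings.** Neither the Schedule of assessments nor 8.2.3 says that scheduled ECGs are taken in triplicate. Two extra ECGs to confirm one measurement imply that they are single.

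**Mixed terms within 8.2.3.** The rule for ending hourly ECGs speaks of QT and QTcF together. Cardiologist consultation depends on QTcF returning below criteria of which one is a QT criterion. The provision that repeats may be unnecessary after a medical reading refers to a prolonged QTc as previously defined, but the only absolute 500 msec limit given before it in that section is in QT.

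**Elsewhere.** The Screening exclusion ("QTcF interval > 450 msec, QRS interval > 120 msec"), Protocol Table 8 and SAP Table 3 all use QTcF.

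**The concern.** Limb (a) of the trigger and the second stopping criterion are the same condition. Limb (b) looks like the counterpart of the first stopping criterion, since both carry the figure 500 msec, but it is in a different unit. Under Fridericia's correction the two agree only at 60 bpm. Above that rate, QTcF reaches 500 msec while QT is still lower, and limb (b) stays silent. Below it, limb (b) fires while QTcF is still under 500 msec.

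The stopping rule needs three readings. If the trigger does not fire, nothing obliges the site to take the other two, so a mandatory rule may have no data to act on. In the other direction, a subject with a slow heart rate can enter repeat and then continuous monitoring at a QTcF well short of the stopping value.

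**Working it through.** The plan gives no figure to reproduce here, so the check sets the two rules against each other.

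**Inputs**
- Trigger limbs (a) and (b): Protocol 8.2.3.
- Stopping criteria: Protocol 7.1.1.
- Screening QTcF limit of 450 msec: Protocol 5.2, exclusion 13.
- Baseline: last non-missing value before first dose, SAP 4.3.1. The scheduled ECG closest to dosing is Day 1 pre-dose.
- Fridericia: QTcF = QT / (60/HR)^(1/3), so QT = QTcF × (60/HR)^(1/3).

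**Step 1: how far QT and QTcF differ at 500 msec**

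| Heart rate (bpm) | QT when QTcF = 500 (msec) | QTcF when QT = 500 (msec) |
|---|---|---|
| 50 | 531 | 471 |
| 60 | 500 | 500 |
| 65 | 487 | 514 |
| 75 | 464 | 539 |
| 90 | 437 | 572 |

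At 75 bpm, for example, 500 × (60/75)^(1/3) = 464 msec. On its own, limb (b) would miss a QTcF of 500 msec at any rate above 60 bpm.

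**Step 2: what limb (a) catches.** If baseline QTcF is 440 msec or less, a reading of 500 msec is a rise of at least 500 − 440 = 60 msec and is above 450 msec. Limb (a) therefore fires.

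**Step 3: what is left.** A reading at the stopping value escapes both limbs only if all of these hold:
- baseline QTcF is above 440 msec;
- heart rate is above 60 bpm;
- QTcF is at least 500 msec but below baseline + 60 msec, and QT is still below 500 msec.

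The width of the band is at most (baseline + 60) − 500 = baseline − 440:
- baseline 445: 500 to <505 msec, width 5;
- baseline 450: 500 to <510 msec, width 10.

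Very close to 60 bpm the band is narrower, because limb (b) takes over: at 61 bpm it fires from QTcF 502.8 msec. By 65 bpm it fires only from about 514 msec, so the full 10 msec band is open at baseline 450.

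A grid search in steps of 1 msec and 1 bpm (baseline 380–465, heart rate 50–100, post-dose QTcF 450–540) found no gap at any baseline of 440 or less and none at 60 bpm or below.

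**Step 4: worked example.** Baseline QTcF 445, heart rate 75 bpm, QT 466:
- QTcF = 466 / (60/75)^(1/3) = 502 msec.
- Rise = 502 − 445 = 57 msec, below 60, so limb (a) is not met.
- QT = 466 msec, below 500, so limb (b) is not met.

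With baseline 430 and the same ECG, the rise is 72 msec and limb (a) fires.

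**Step 5: the reverse case.** QT 500 at 50 bpm gives QTcF 471 msec. Limb (b) fires at a QTcF 500 − 471 = 29 msec below the first stopping value, whatever the baseline.

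**Step 6: where it can change dosing.** PART-1 is single-dose and its only scheduled post-dose ECG is on Day 11, so no later dose can be stopped. In PART-2, the scheduled ECGs that precede a remaining dose are Day 4 pre-dose, Day 4 at 3 hours and Day 7 pre-dose.

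**The case against.** The strongest reply is that limb (a) already does most of the work. It is in QTcF, it matches the second stopping criterion, and it closes the gap completely up to a baseline of 440 msec. This stands, and it sets the size of the point. From the QT values in Step 1 alone, a reader might infer that the trigger fails generally at ordinary heart rates. The documents do not support that.

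A second reply is that a reading of 502 msec would not pass unnoticed. Protocol 8.2.3 requires every ECG to be assessed for QTcF prolongation. Section 7.1.1 obliges the investigator to decide on continuation after a clinically significant finding, and Section 8 asks for immediate discussion of safety issues with the sponsor. Additional ECGs are allowed at any time, and abnormal ones may be repeated. It would therefore be too strong to call the 8.2.3 trigger the only route to three readings. What remains is that these provisions require review or permit repeats; none requires the triplicate.

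Third, the reverse mismatch errs toward more monitoring, and the medical-reading provision may allow repeats to be waived, although its wording does not clearly reach an uncorrected QT. This softens the consequence but leaves the text unclear.

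Two further inferences should be avoided. The 50 bpm used above is an illustration and not a floor for on-study heart rate: exclusion 11 applies at Screening and joins blood pressure to pulse rate with an and. Appendix 6, with its list headed "ECG findings that may qualify as serious adverse events", classifies events for reporting. It need not share a boundary with a stopping rule, and no conflict there is needed for this point.

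**Conclusion.** The inconsistency between Protocol 8.2.3 and 7.1.1 is real and its practical reach is small. For baseline QTcF above 440 msec and heart rate above 60 bpm, a single QTcF of 500 msec or slightly more can occur without the repeats needed to evaluate the stopping rule. The missed band is at most 5 msec wide at baseline 445 and 10 msec at baseline 450. In the other direction, slow heart rates bring in monitoring at a QTcF below the stopping value. Any effect on later dosing is confined to PART-2.

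A reader might infer that a subject can meet the stopping rule undetected. Strictly that is not so: the rule applies to a triplicate average, and a single reading cannot meet it. The defect is that the average need not be obtained.

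The conclusion assumes that scheduled ECGs are single, which the text implies but does not state, and that the site uses the SAP's baseline. The 450 msec limit is stated for Screening only. If a Day 1 pre-dose baseline exceeded it, the band would be wider, for example up to 15 msec at 455. The documents give no distribution of baseline QTcF or heart rate, so the expected number of affected subjects cannot be calculated.

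**What to change.** Reconcile Sections 8.2.3 and 7.1.1 in the next amendment so that:
- the repeat trigger, the continuous-monitoring trigger and the first stopping criterion refer to the same interval;
- any single reading at the stopping value leads to the triplicate that 7.1.1 needs;
- the mixed QT, QTc and QTcF terms in 8.2.3 (hourly repeats, cardiologist consultation, waiver of repeats) are made consistent.

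Which interval and value apply is for the sponsor's clinicians; this review takes no position. If limb (b) and the first stopping criterion used the same interval and boundary, no reading at that boundary would escape the repeats.

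The cost is a wording change, with no added visits or scheduled ECGs. Appendix 6 needs no change for this point.

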8.2.4 Clinical safety laboratory assessments

See [Appendix 2](#) for the list of clinical safety laboratory tests to be performed, and the [Schedule of assessments](#) for the timing and frequency. Unscheduled clinical laboratory measurements may be obtained at any time during the study to assess any perceived safety issues.

The Investigator must review the laboratory report, document this review, and record any clinically significant changes occurring during the study in the AE section of the eCRF. Clinically significant abnormal laboratory findings are those which are not associated with the underlying disease, unless these are judged by the Investigator to be more severe than expected for the subject's condition.

All laboratory tests with values considered clinically significantly abnormal during participation in the study or within 28 – 35 days after the last dose of study drug should be repeated until the values return to normal or baseline or are no longer considered clinically significant by the Investigator.

If such values do not return to normal or baseline within a period of time judged reasonable by the Investigator, the etiology should be identified and the Sponsor notified.

See [Appendix 5](#) for suggested actions and follow-up assessments in the event of potential drug-induced liver injury (DILI).

The clinical safety laboratory data, including date and time of assessment, are to be recorded in the eCRF.

8.2.5 Pregnancy testing

Pregnancy tests may be urine or serum tests, but must have a sensitivity of at least 25 mIU/mL. Pregnancy tests are to be performed for women of childbearing potential at the times listed in the [Schedule of assessments](#). Following a negative pregnancy test result at Screening, appropriate contraception must be commenced and a second negative pregnancy test result will be required at Day –1 prior the subject receiving the first study

drug. Pregnancy tests must also be done whenever one menstrual cycle is missed during the active collection period (or when potential pregnancy is otherwise suspected), and at the end of the study. If a urine test cannot be confirmed as negative (e.g., the result is ambiguous), a serum pregnancy test is required.

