- e. A complete physical examination must be performed by trained medical personnel at Screening, and a brief physical examination must be performed at all the other time points (see Section 8.2.1).
- f. Height is to be measured at Screening only to obtain BMI.
- g. Blood for safety laboratory tests (hematology, clinical chemistry, and urinalysis) should be taken after at least 4 hours of fasting during Screening, Day -1, pre-dose (within 30 minutes before study drug administration) on Day 7, on the last observation day (Day 22) morning, and at Early discontinuation, if applicable. On Day 1 and Day 4, blood for safety laboratory tests should be taken at 3 hours (± 30 minutes) after dose administration/start of infusion in the morning, without fasting. Additional safety laboratory assessments may be performed at any time at the discretion of the Investigator.
- h. Pregnancy tests (urine or serum) are to be performed for women of childbearing potential only (see Section 8.2.5).
- i. The Investigator must discuss with the subject at Screening, Day -1, Day 11 (before discharge), and at Follow-up, the need to use highly effective contraception consistently and correctly in accordance with the contraception guidelines (see Section 5.3.4 and [Appendix 4](#)).
- j. For postmenopausal (amenorrheic for at least 12 consecutive months) female subjects only.
- k. Urine drug test may be performed at any other time at the discretion of the Investigator.
- l. 12-lead ECGs and vital signs should be conducted during Screening, on Day 1 prior to dosing in the morning (within 2 hours of study drug administration), pre-dose on Day 4 and Day 7, at 3 hours (± 30 minutes) after dose administration/start of infusion on Day 4, in the morning on Day 22, and at Early discontinuation, if applicable. All ECG assessments and vital signs tests are to be made after at least a 5-minute rest in a supine position. The order is ECG assessment before vital signs and before any blood draws. Additional ECGs and vital signs (BP, PR, temperature, respiratory rate, oxygen saturation) may be performed at any time at the Investigator's discretion.

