8 STUDY ASSESSMENTS AND PROCEDURES

The Investigator or designee must obtain a signed and dated ICF before performing any study-specific procedures.

Study procedures and their timing are summarized in the [Schedule of assessments](#). Protocol waivers or exemptions are not allowed.

Safety issues should be discussed with the Sponsor immediately to determine whether the subject should continue or discontinue study drug.

All screening evaluations must be completed and reviewed to confirm that potential subjects meet all eligibility criteria. The Investigator must maintain a screening log to record details of all subjects screened, and to confirm eligibility or record reasons for screening failure, as applicable.

Subjects will be screened within 28 days prior to administration of the first study drug to confirm that they meet the study population criteria for the study. If the time between screening and dosing exceeds 28 days as a result of unexpected delays (e.g., delayed drug shipment), then subjects do not require rescreening if the laboratory results obtained prior to first dose administration meet the eligibility criteria.

Every effort should be made to ensure that protocol-required tests and procedures are completed as described. However, it is anticipated that from time to time there may be circumstances outside the control of the Investigator that may make it unfeasible to perform the test. In these cases, the Investigator must take all steps necessary to ensure the safety and wellbeing of the subject. When a protocol-required test cannot be performed, the Investigator must document the reason for the missed test and any corrective and preventive actions taken to ensure that required processes are adhered to as soon as possible. The Sponsor study team must be informed of these incidents in a timely manner.

If an IV catheter is utilized for blood sample collections, ECGs and vital sign assessments should be collected prior to the insertion of the catheter.

For samples being collected and shipped, detailed collection, processing, storage, and shipment instructions and contact information will be provided to the clinical site prior to initiation of the study.

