8.3.1 Time period and frequency for collecting AE and SAE information

The time period for actively collecting AEs and SAEs (the ‘active collection period’) for each subject begins from the time the subject provides informed consent, through and including 28 – 35 days after the last administration of the study drug.

If there is an unresolved AE at the end of the active collection period, follow-up by the Investigator continues until the AE or its sequelae resolve or stabilize at a level acceptable to the Investigator. After follow-up visit, information on AEs will only be recorded on source documents (except in case of SAE as described in Section 8.3.1.1).

For subjects who are screen failures, the active collection period ends when screen failure status is determined.

If the subject withdraws from the study and also withdraws consent for the collection of future information, the active collection period ends when consent is withdrawn.

If a subject temporarily or permanently discontinues study drug because of an AE, the AE must be recorded in the eCRF, and if an SAE, must also be reported using the SAE Report Form.

The Investigator is not required to actively seek information on AEs after the subject has concluded study participation. However, if the Investigator learns of any SAE, including a death, at any time after a subject has completed the study, and considers the event to be reasonably related to the study drug, the Investigator must promptly report the SAE to the Sponsor using the SAE Report Form.

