Appendix 4 Contraception

1. Male subject reproductive inclusion criteria

No contraception methods are required for male participants in this study, as the calculated safety margin is ≥ 100 -fold between the estimated maternal exposure due to seminal transfer and the NOAEL for serious manifestations of developmental toxicity in nonclinical studies.

2. Female subject reproductive inclusion criteria

A female subject is eligible to participate in the study if she is not pregnant or breastfeeding, and at least one of the following conditions applies:

- The subject is not a woman of childbearing potential (WOCBP) (see definition [below](#)).
OR
- The subject is a WOCBP and is using a contraceptive method that is highly effective (with a failure rate of $< 1\%$ per year), preferably with low user dependency, as described below from Screening until Follow-up visit, and for at least 28 days after the last dose of study drug, which corresponds to the time needed to eliminate any reproductive safety risk of the study drug. The Investigator should evaluate the effectiveness of the contraceptive method at Screening prior to the first dose of study drug.
OR
- The subject is a WOCBP and is using a contraceptive method that is highly effective (with a failure rate of $< 1\%$ per year), with high user dependency, as described below from Screening until Follow-up visit, and for at least 28 days after the last dose of study drug, which corresponds to the time needed to eliminate any reproductive safety risk of the study drug. In addition, a second effective method of contraception must be used. The Investigator must evaluate the effectiveness of the contraceptive method at Screening prior to the first dose of study drug.

The Investigator is responsible for reviewing the subject's medical history, menstrual history, and recent sexual activity to decrease the risk of the inclusion in the study of a woman with an early undetected pregnancy.

3. Woman of childbearing potential

A woman is considered to be a WOCBP following menarche and until becoming postmenopausal unless permanently sterile (see below).

If fertility is unclear (e.g., amenorrhea in adolescents or athletes) and a menstrual cycle cannot be confirmed before the first dose of study drug, additional evaluation should be considered.

4. Women not considered to be of childbearing potential

A woman in any of the following categories is not considered to be a WOCBP:

- Premenopausal with one of the following:

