### 4.3.2 Study day calculation and visit windows

Visit windowing approaches will not be used for this study, and visit based summaries will include scheduled assessments only.

The following conventions will be used to calculate analysis study day:

- Day 1 is the day of first study drug administration. Day -1 is the day before Day 1. No Day 0 is defined for this study.

- Prior to Day 1, the algorithm is:  
Study Day = visit/examination date – date of first study drug administration
- For Day 1 and subsequent days, the algorithm is:  
Study Day = visit/examination date – date of first study drug administration + 1.

Summary data such as AEs will not be reported by visit.

Both scheduled and unscheduled visits and assessments will be used to determine minimum and maximum change from baseline. Tables that report abnormalities (e.g., laboratory shift tables) will include all assessments.

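### No minimum time is set between starting contraception and the Day -1 pregnancy test, so a recent conception can test negative twice before dosing

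*Protocol*

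**What the plan says.** **Testing.** Protocol Section 8.2.5 reads: "Following a negative pregnancy test result at Screening, appropriate contraception must be commenced and a second negative pregnancy test result will be required", the second test being on Day -1, before the first dose. Urine or serum tests are allowed, with a sensitivity of at least 25 mIU/mL. In Section 1.3 both parts place Screening anywhere from Day -28 to Day -2. Scheduled pregnancy tests are at Screening, on Day -1, on Day 11 (PART-1) or Day 22 (PART-2), and at early termination.

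**Limits on timing.** Section 8 gives only an upper limit: screening within 28 days before the first dose, with an allowance "If the time between screening and dosing exceeds 28 days as a result of unexpected delays". No lower limit appears anywhere, and no test is tied to the menstrual cycle.

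**Contraception.** One route to eligibility in Appendix 4 is: "The subject is a WOCBP and is using a contraceptive method that is highly effective". The period of use is given "as described below from Screening until Follow-up visit", and for at least 28 days after the last dose. No use before Screening is required.

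**Safeguards.**
- The Investigator reviews recent sexual activity and menstrual history, with early undetected pregnancy expressly in mind, and evaluates the method's effectiveness at Screening (Appendix 4).
- User-dependent methods need an added barrier (Appendix 4).
- Section 5.3.4 and the schedules add contraception checks. The PART-2 footnote reads: "The Investigator must discuss with the subject at Screening, Day -1, Day 11 (before discharge), and at Follow-up".
- Section 8.2.5 requires an extra test after a missed cycle or on suspicion of pregnancy during the active collection period, which "begins from the time the subject provides informed consent" (Section 8.3.1).

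**The concern.** A second pregnancy test is useful because it comes later than the first: it can catch a conception too recent for the first test to detect, provided contraception has prevented new conceptions in between. Its value therefore depends on how much time separates the start of effective contraception from the second test. The protocol leaves that time open. On the shortest permitted schedule the second test adds a single day of detection.

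The stake is fetal exposure. Section 4.2.1 describes a nonclinical signal of severe developmental harm at exposures relevant to clinical use. Table 2 relies on excluding pregnant women and on contraception as mitigation. Section 2.3 expects no clinical benefit for these healthy volunteers, so nothing for the subject offsets such an exposure. The scheduled tests after Day -1 fall after all dosing and cannot prevent it.

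**Working it through.** The plan gives no figure of its own to reproduce. The check is calendar arithmetic.

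**Inputs from the documents**
- Screening window Day -28 to Day -2, second test on Day -1 (Protocol Section 1.3, both parts).
- Day numbering: "No Day 0 is defined for this study" (SAP Section 4.3.2), so Day -1 is one day before Day 1.
- A method may start at Screening (Section 8.2.5; Appendix 4).

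**Assumptions not in the documents**
- L, the days from conception to a positive test: 8 to 16, with 7 and 21 as wider values.
- The method is fully effective from the day it starts. This favours the protocol; a slower onset would enlarge the results.

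**Formulas**
- For Screening on Day -s with the method started that day, the time from start to the Day -1 test is T = s - 1 days.
- A conception c days before the start of the method (c = 0 on that day) is T + c days old at the Day -1 test. It is missed if T + c < L, and it was then also too recent for the Screening test. The number of missed conception days is max(0, L - T).

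**Results**

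| Screening and method start | T (days) | Missed, L = 8 to 16 | Missed, L = 7 | Missed, L = 21 |
|---|---|---|---|---|
| Day -2 | 1 | 7 to 15 | 6 | 20 |
| Day -7 | 6 | 2 to 10 | 1 | 15 |
| Day -15 | 14 | 0 to 2 | 0 | 7 |
| Day -17 | 16 | 0 | 0 | 5 |
| Day -28 | 27 | 0 | 0 | 0 |

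With Screening on Day -2, the first dose follows 2 days after the method starts.

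**Which interval matters.** T runs from the start of the method, not from the Screening test. Suppose a woman starts on Day -3 and is screened on Day -2. Then T = 2 and the missed days are 8 - 2 = 6 to 16 - 2 = 14, hardly better than 7 to 15. Having a method in place before Screening is therefore not enough without a minimum duration.

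**The case against.** **Day -2 is an unlikely schedule.** Section 5.3.1 bars red wine and grapefruit from 7 days before the first dose, and Section 5.3.3 bars strenuous exercise for 48 hours before laboratory draws. Section 8 requires subjects to be instructed on these restrictions, and all screening results, including serology, to be reviewed before eligibility is confirmed. These rules press Screening earlier. They do not prohibit Day -2, because a subject may already have abstained. Taking Day -7 as the more plausible late case still leaves 2 to 10 missed days.

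**The protocol already recognises early undetected pregnancy.** It assigns that risk to Investigator judgement, supported by evaluation of the method and by contraception checks. This stands as real mitigation. However, history review depends on recall and judgement and carries no timing rule, while contraception measures prevent new conceptions and cannot detect one already present. A missed-cycle test may come only after dosing has begun.

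**The proposed length rests on an assumed lag.** This is correct. At L = 21, a 16-day minimum leaves 5 missed days and a 14-day minimum leaves 7. The sponsor should set the figure.

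**Stronger readings that a reader might infer**
- *That Section 8.2.5 contradicts Appendix 4.* The former has contraception begin after a negative Screening test, while the latter describes a woman already using a method. A woman who starts on the day of Screening satisfies both.
- *That a scheduled test is missing during dosing.* The next tests do fall on Day 11 and Day 22, after dosing. But PART-1 has a single dose, and in PART-2 an extra test could act only after exposure had begun. This is a separate matter that the present fix does not address.
- *That the PK results are compromised.* Nothing in the documents supports this.

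**Conclusion.** The point holds in limited form. The protocol sets no minimum time between starting contraception, or the Screening test, and the Day -1 test. For a woman of childbearing potential who starts a method at Screening, that time can be as short as 1 day.

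The absence of a minimum and the 1-day case come directly from the documents. The counts of missed days depend on the assumed lag of 8 to 16 days and on immediate effectiveness of the method, but for any lag above 1 day some conceptions are missed at the shortest interval. The number of women affected is not given and may be small.

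This is an inexpensive safety improvement, between worth considering and something that should be done. It does not show that the protocol lacks safeguards, or that late screening is expected to be common.

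**What to change.** In Section 8.2.5 and, in matching words, Appendix 4, require every woman of childbearing potential to have used a highly effective method, confirmed by the Investigator, for at least a stated minimum before the negative Day -1 test. Apply the rule whether the method was started before or at Screening, so that starting one day before Screening does not avoid it.

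Sixteen days would cover the lag range assumed here; the sponsor should set the figure from the detection lag of the assay used. With 16 days, a woman who starts at Screening must be screened by about Day -17. The existing window can accommodate a minimum of up to 27 days (Screening on Day -28). A woman with long enough prior use could still be screened late.

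The cost is a wording change in two places, and a few women screened earlier or deferred. No test or visit is added, and the SAP needs no change.
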